8.5.12 PedsQL-FIM

The PedsQL-FIM, standard version will be tested in Part 2, and will be performed only for subjects accompanied by their family, caregiver or equivalent thereof. The PedsQL-FIM will be performed to assess specifically caregiver's and family's burden. In the eCRF, whether or not a test has been performed as well as the date and results of the test should be recorded.

Rationale for this Exploratory Assessment

This assessment was selected to explore how the QoL has changed, because it is known that burden of caregiver and family of patients with MPS I is high and gathering data of QoL is important.

8.5.13 Status of Cross-Reactive Immunologic Material (CRIM)

A blood specimen and fibroblasts will be collected once in the JR-171-101 study from subjects who agreed to the sample collection to determine the CRIM status, and the samples will be obtained before the JR-171 administration during the visit. The sample collection date should be recorded in the eCRF. The assay for the CRIM status will be performed by the laboratory under contract with the sponsor.

Rationale for this Exploratory Assessment

This assessment was selected to evaluate the impact of the CRIM status on the PKs, pharmacodynamics, safety and efficacy endpoints.

9. Statistical Considerations

9.1 Statistical Hypotheses

For the exploratory endpoint analyses, a paired sample t-test will be conducted on HS and DS concentrations in CSF. The quantity of interest is the mean change from baseline. The null hypothesis for comparison (H_0) with threshold value of delta (Δ) and the alternative hypothesis of effect of JR-171 (H_1) are defined as follow, where μ denotes mean change from baseline in HS or DS concentrations in CSF and Δ = 0.

 H_0 : $\mu = \Delta$

 H_1 : $\mu > \Delta$ or $\mu < \Delta$.

No hypothesis testing is planned for the other exploratory endpoints, safety and PK assessments.

9.2 Sample Size Determination

Part 1: 4 subjects (18 years or older)
Part 2: Approximately 15 subjects in total

Rationale for the Target Sample Size

In this first-in-human study of JR-171, adult patients (18 years old or older) with mild MPS I who can report their own subjective symptoms are deemed appropriate to confirm the safety of JR-171 in Part 1. MPS I is an extremely rare disease, which is estimated to have the birth prevalence of approximately 0.11 to 3.62 per 100000 live births.²⁾ In addition, 60.9% of the patients are reported to have severe disease manifestations with intellectual disability,³⁾ indicating that there may be very few adult patients with mild MPS I who have little or no intellectual disability. Based on these considerations and the target sample size of 4 subjects was selected for Part 1 in view of feasibility.

In Part 2, pediatric patients will be able to participate since treatment of MPS I often starts in childhood. It is assumed that only a small number of patients could undergo lumbar puncture. Furthermore, it is reported that 54.9% of severe MPS I patients have a history of HSCT.⁸⁾ Therefore, it is assumed only a very limited number of patients would be eligible to participate in the study. Based on these considerations and in view of feasibility, the target sample size of approximately 15 subjects was selected to evaluate the safety and efficacy of JR-171.

9.3 Populations for Analyses

The following populations are defined:

Population	Description
Safety set (SS)	All subjects who sign the ICF.
Pharmacokinetic set (PKS)	Subjects assigned to study intervention and have data for plasma drug concentration after administration of JR-171.
Full analysis set (FAS)	Subjects assigned to study intervention and have data for at least one exploratory endpoint after administration of JR-171

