8.3.1 Time Period and Frequency for Collecting AE and SAE Information

All AEs and SAEs will be collected from the time of informed consent until the last visit (Week 5 in Part 1/Week 13 in Part 2, or discontinuation) at the time points specified in the Schedule of Activities (see Section 1.3). Events occurring within 28 days after the time of observation at Week 5 in Part 1/Week 13 in Part 2 or discontinuation that are considered related to the investigational product will be collected as adverse drug reactions in the JR-171-101 study, except for events that are occurred during the extension study of the JR-171-101 study (JR-171-102). In the eCRF, presence or absence of AEs and, if applicable, its details (Appendix 2 (see Section 10.2.4)) should be recorded.

Data of MPS I-related medical occurrences that begin before obtaining informed consent will be recorded in the Medical History/Current Medical Conditions section of the case report form not in the AE section.

All SAEs will be recorded and reported to the sponsor immediately and under no circumstance should exceed 24 hours, as indicated in Appendix 2 (see Section 10.2). The principal investigator will submit any updated SAE data to the sponsor within 24 hours of it being available.

Principal investigators are not obligated to actively seek AEs or SAEs after conclusion of the study participation. However, if the principal investigator learns of any SAE, including a death,

at any time after a subject has been discharged from the study, and he/she considers the event to be reasonably related to the study intervention or study participation, the principal investigator must promptly notify the sponsor.

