9.4 Statistical Analyses

The statistical analysis plan will be finalized prior to First Patient First Visit, and it will include a more technical and detailed description of the statistical analyses as well as the handling of subjects and individual data determined in consultation with the medical and statistical experts as appropriate. This section is a summary of the planned statistical analyses of the most important endpoints including primary and key secondary endpoints.

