9.4.3 Safety Analyses

This section outlines the planned safety analyses in the JR-171-101 study. Safety analyses will be performed on the SS.

All AEs will be coded to PT and system organ class (SOC) using the latest version of the Medical dictionary for regulatory activities terminology (MedDRA).

All AEs occurred after the first dose of JR-171 will be considered as treatment-emergent AEs and will be summarized by study period and dose group. For each study period and dose group, the incidence proportion of AEs will be summarized with frequency and percentage by MedDRA SOC and PT.

AEs occurring before the first dose of JR-171, include AEs that occurred in screen failure, will be pooled regardless study period or dose group and summarized in the same way.

For laboratory tests, summary statistics of measured values at each time point as well as changes from baseline will be calculated for Part 1 and each group in Part 2, and time courses

or shift tables will be created for each subject.

For vital signs, summary statistics of measured values at each time point as well as changes from baseline will be calculated for Part 1 and each group in Part 2, and time courses will be created.

For 12-lead electrocardiogram, the presence or absence of abnormality will be tabulated.

For antibody tests, shift tables will be created with respect to the presence or absence of antibody development at each time point.

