10.2.1 Definition of AE

AE Definition

An AE is any untoward or unintended illness or its sign (including an abnormality observed in laboratory tests or physiological tests) in a subject, which does not necessarily have to have a causal relationship with the investigational product. AEs that occur after the administration of an investigational product, those that have an undeniable causal relationship with the investigational product are considered adverse drug reactions.

- Any patient having received any amount of investigational product should be evaluated for safety. The schedule of assessments is shown in the Schedule of Activities, Section 1.3.
- Any AE must be documented and the following guidelines will be used for this purpose. An AE is the development of an undesirable medical condition or the deterioration of a pre-existing medical condition following or during exposure to a pharmaceutical product, whether or not considered causally related to the product. An undesirable medical condition can be symptoms (e.g., nausea, chest pain), signs (e.g., tachycardia, enlarged liver) or the abnormal results of an investigation (e.g., laboratory findings, electrocardiogram). In clinical studies, an AE can include an undesirable medical condition occurring at any point of time after the patient consented to participate. This definition includes intercurrent illnesses or injuries, and exacerbation of pre-existing conditions.
- Where a diagnosis is possible, it is preferable to record it in the eCRF rather than as a series of terms relating to the diagnosis.
- An event that is solely due to progression of disease should not be reported as AEs.

Events Meeting the AE Definition

- Any abnormal laboratory test results (hematology, clinical chemistry, or urinalysis) or other safety assessments (e.g., ECG, radiological scans, vital signs measurements), including those that worsen from the time of informed consent, considered clinically significant in the medical and scientific judgment of the principal investigator or subinvestigator (i.e., not related to progression of underlying disease).
- Exacerbation of a chronic or intermittent pre-existing condition including either an increase in frequency and/or intensity of the condition.
- New conditions detected or diagnosed after study intervention administration even though it may have been present before the start of the study.

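### The safety set is defined by consent alone, so, read literally, a registered but never-dosed subject lowers the treatment-emergent AE percentages

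*Combined protocol and SAP*

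**What the plan says.** The table in Section 9.3 defines the safety set (SS) as "All subjects who sign the ICF". The other two sets in that table, the pharmacokinetic set and the full analysis set, both require data obtained after JR-171 was given. Only the SS has no link to dosing.

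Section 9.4.3 then states: "Safety analyses will be performed on the SS". It defines the events of interest by exposure: "All AEs occurred after the first dose of JR-171 will be considered as treatment-emergent AEs". It reports them as follows: "For each study period and dose group, the incidence proportion of AEs will be summarized with frequency and percentage by MedDRA SOC and PT". It names no denominator other than the SS and no treated subset.

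Earlier events are handled separately in the same section: "AEs occurring before the first dose of JR-171, include AEs that occurred in screen failure, will be pooled regardless study period or dose group". This fits the collection rule in Section 8.3.1: "All AEs and SAEs will be collected from the time of informed consent until the last visit".

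Section 10.2.1 contains an exposure-based statement, "Any patient having received any amount of investigational product should be evaluated for safety". It is part of the AE definition, sets no denominator, and is not taken up in Section 9.3.

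**The concern.** One set serves two purposes that need different denominators. A consent-based set suits the pooled summary of events before dosing. It does not suit treatment-emergent percentages, because a subject who never received JR-171 cannot have a treatment-emergent event.

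Frequency of AEs is a primary endpoint (Section 3) and the groups are very small, so one such subject visibly changes a reported percentage. The change can only be downward, which for safety is the non-conservative direction. If the undosed subject falls in only one of the two Part 2 dose groups, the descriptive comparison between 2.0 and 4.0 mg/kg shifts as well.

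**Working it through.** The plan gives no AE rate, expected event count or explicit denominator, and Section 9.2 bases the sample size on feasibility. There is therefore no planned figure to reproduce. The check traces the definitions and then sizes the effect.

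**Can a subject be registered, and in Part 2 allocated, without being dosed?**

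- Section 1.3, Part 2 schedule: allocation to a treatment group is marked at Registration, before the Baseline and Week 1 columns. A randomized subject can therefore hold a dose group without having had a dose.
- Section 1.3, Part 1 schedule: there is no allocation row, but a registered subject still belongs to the Part 1 study period.
- Section 10.2.4 foresees withdrawal before the first administration.
- Section 5.4 limits screen failures to consented subjects who were not registered. A registered, undosed subject is not a screen failure.
- Section 7.2 says that withdrawn subjects are not replaced, so such a subject takes one of the planned places.

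**Inputs for the size of the effect**

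- Part 1: 4 subjects (Section 9.2).
- Part 2: approximately 15 in total (Section 9.2), with at least 2 escalation subjects and at least 6 in each randomized group (Section 1.2). About 15 - 2 = 13 are randomized, or 6 to 7 per group.
- Number undosed (u) and number of subjects with the event (x): assumptions, because the documents give neither.

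**Formulas**, with n the number registered or allocated:

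- Dosed-only percentage = x/(n-u)
- Literal SS percentage = x/n
- Ratio of literal to dosed-only = (n-u)/n
- Largest gap, when every dosed subject has the event (x = n-u): 1 - (n-u)/n = u/n

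| Setting | n | u | x | Dosed-only | Literal SS | Factor | Gap (points) |
|---|---|---|---|---|---|---|---|
| Part 2, larger group | 7 | 1 | 3 | 3/6 = 50.0% | 3/7 = 42.9% | 6/7 = 0.857 | 7.1 |
| Part 2, smaller group | 6 | 1 | 2 | 2/5 = 40.0% | 2/6 = 33.3% | 5/6 = 0.833 | 6.7 |
| Part 1 | 4 | 1 | 2 | 2/3 = 66.7% | 2/4 = 50.0% | 3/4 = 0.750 | 16.7 |
| Any group | n | 0 | x | x/n | x/n | 1.000 | 0 |

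With one undosed subject the largest possible gap is 1/7 = 14.3 points, 1/6 = 16.7 points and 1/4 = 25.0 points, respectively.

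**The case against.** The strongest reply is that the denominator is inferred. Section 9.4.3 never says that percentages are taken over every SS member. It splits events at the first dose, and the dose-group columns could be read as holding only subjects dosed in that group. Section 9.4 also describes itself as a summary and leaves to a separate SAP "the handling of subjects and individual data determined in consultation with the medical and statistical experts as appropriate"; that SAP is not among the documents. Section 9.4.1.5 refers to a further document on adopting data and subjects, though in the context of unusable values.

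Part of this stands. The dosed-only reading is possible, and the SAP may already state it. But the split in 9.4.3 says where events are reported and removes nobody from the treatment-emergent denominator. A SAP rule that differs from the stated SS definition would leave the two texts in conflict.

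It is also fair that the opportunity is limited. Under Section 6.6.1, second and later children are assigned only after safety is confirmed in the first subject of their age group, so allocated children do not wait undosed for that step. No document gives an expected number of undosed subjects.

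A reader might infer that screen failures also dilute the dose-group percentages, since they sign the ICF. The documents do not support that: screen failures carry no dose group, and their AEs go to the separate pooled summary. A reader might also infer that safety decisions would be distorted. That does not follow either. Section 9.1 plans no safety test, counts appear beside percentages, and the escalation and termination triggers in Sections 6.6.1 and 7.1.1 do not use these percentages.

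**Conclusion.** The point holds as a matter of definition. As written, Sections 9.3 and 9.4.3 together place a registered but never-dosed subject in the denominator of treatment-emergent AE percentages. The case is clearest for randomized Part 2 subjects and weaker for Part 1, where no dose group is allocated.

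With one undosed subject, the reported percentage is 0.833 to 0.857 of the dosed-only percentage in a Part 2 group, and 0.75 of it in Part 1. These factors rest on the planned sizes, no replacement, the literal reading of the SS and an assumed u = 1. If every registered subject is dosed, the effect is nil.

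The consequence is confined to descriptive percentages, so the severity is minor. Section 9.4.3 specifies no percentage for infusion associated reactions (IARs); one produced under the general SS rule would be affected in the same way.

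**What to change.** Define the SS as all subjects who received any amount of JR-171, in line with Section 10.2.1. Use it as the denominator for treatment-emergent AEs and for any other post-dose safety percentage, including IARs if one is reported. Keep a separate all-consented set for the pooled pre-dose AE summary only. Make Sections 9.3 and 9.4.3 and the separate SAP agree; if the SAP already uses a dosed-subject denominator, align 9.3 with it.

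The change is a few lines, with no new data and no change in conduct. Because the Statement of Compliance requires IRB approval of any protocol amendment, the wording can be carried in the SAP or held for the next routine amendment. The one downside is that reported AE percentages will be somewhat higher if any registered subject is never dosed.

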9.4 Statistical Analyses

The statistical analysis plan will be finalized prior to First Patient First Visit, and it will include a more technical and detailed description of the statistical analyses as well as the handling of subjects and individual data determined in consultation with the medical and statistical experts as appropriate. This section is a summary of the planned statistical analyses of the most important endpoints including primary and key secondary endpoints.

9.4.1 General Considerations

9.4.1.1 Significance Level and Confidence Interval

Unless otherwise specified, all statistical tests will be 2-sided hypothesis tests performed at the 5% level of significance and all confidence intervals will be 2-sided 95% confidence intervals. All statistical tests and confidence intervals will be parametric assuming normally distributed sample means.

9.4.1.2 Definitions of Baseline

Unless otherwise specified, the baseline value will be defined as the measurement prior to and closest to the date of the first dose of JR-171.

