1.3 Schedule of Activities

Part 1

Observation/test timing	Pre-screening	Screening test	Registration	Baseline	Week 1	Week 2	Week 3	Week 4	Week 5	Discontinuation
Visit window	-	28 days before Day 1 (Day -28) to Day -7	-	Day -2 to Day 1	Day 1	Day 8 to Day 11	Day 15 to Day 18	Day 22 to Day 25	Day 29 to Day 32	Within 28 days from discontinuation
JR-171 administration					Х	Χ	Х	Χ		
Informed consent	X									
Subject baseline characteristics ^{a)}		Х								
Assessment based on			Х							
inclusion/exclusion criteria			^							
Pregnancy testing (female subjects of childbearing potential only)		X								
Vital signs ^{b)}		Xc)		X _d)	X ^{e)}	X ^{e)}	X ^{e)}	X ^{e)}	X ^{c), f)}	X _{c)}
Laboratory tests ^{f)}		X		X		X	X	X	X	X
Antibodies ^{f)}				X ^{g)}		X ^{h)}			X ^{g)}	X ^{g)}
Plasma drug concentration ⁱ⁾					Х	X	Х	Х		
Drug concentration in CSF				X ^{f)}				X ^{j)}		X ^{k)}
HS and DS concentrations in CSF				X ^{f)}				X ^{j)}		X ^{k)}
CSF opening pressure				X ^{f)}				X _{j)}		X ^{k)}
Urinary HS and DS concentrations (including measurement of creatinine for concentration adjustment) ⁽⁾				х		Х	Х	Х	Х	х
Serum HS and DS concentrations ^{f)}				Х		Х	Х	Х	Х	X
Liver and spleen volumes ^{f)}				Х					Х	Х
Cardiac function ^{f)}				Х					Х	Х
Other clinical findings related to neurocognitive and behavioral changes										
12-lead electrocardiogram ^{f)}		Χ							Х	X
Cross-reactive immunologic material ⁱ⁾										—
AEs										—
Concomitant therapies/medications					Х	Х	Х	Х	Х	Х

- of JR-171.
- b) Vital signs: pulse rate, body temperature, blood pressure, respiratory rate, percutaneous oxygen g) saturation and body weight. During the infusion of JR-171, it is necessary to monitor other than body h) Anti-JR-171 antibodies weight (see Section 6.1 and 8.2.3).
- c) Excluding body weight
- d) Only body weight is measured.
- e) Perform before and after administration of JR-171 except for body weight. Body weight will be measured at either measuring point.
- a) Neurocognitive testing and adaptive behavior assessment will be performed before the first infusion f) Perform before administration of JR-171 (or before laronidase at Week 5, for subjects who will receive laronidase after completing the JR-171-101 study)
 - Anti-IDUA and anti-JR-171 antibodies

 - Blood specimens should be collected by following the "PK sampling schedule (plasma drug concentration)".
 - Performed within 5 hours after the end of administration of JR-171

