8.5.1 Drug concentration in CSF

Drug concentration in CSF is designated as a centrally measured parameter and measured by the laboratory under contract with the sponsor.

CSF will be collected from each subject once before administration of JR-171 at the initial administration and within 5 hours of the end of administration of JR-171 at Week 4 in Part 1 or Week 12 in Part 2 to measure drug concentration in the CSF. In the case of discontinuation, the measurement will be performed if deemed feasible by the principal investigator or subinvestigator. In the eCRF, whether or not a measurement has been performed and, if applicable, the sample collection date and time should be recorded. For the reporting of results, data should be reported by the laboratory.

Rationale for this Exploratory Assessment

This assessment was selected to confirm the penetration of JR-171 into the CNS.

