8.5.5 Serum HS and DS Concentrations

Serum HS and DS concentrations are designated as centrally measured parameters and will be measured by the laboratory under contract with the sponsor.

Venous blood will be collected from each subject before administration of JR-171 or laronidase to measure serum HS and DS concentrations. Care is to be taken not to contaminate the sample with heparin or heparin-like compounds when collecting samples. In the eCRF, whether or not a measurement has been performed and, if applicable, the sample collection date should be recorded. The measurement results should be reported by the laboratory.

Rationale for this Exploratory Assessment

Given systemic accumulation of HS and DS in patients with MPS I, this assessment was selected to explore the efficacy of JR-171 on systemic symptoms.

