9.4.1.5 Handling of Missing Data

If any value is missing at any time point, they will be handled as missing and will not be imputed. If any value is reported as 'Below the limit of quantification' or the value cannot be used for calculations, handling of these data will be determined in a separate document which describes standard of adoption for data and subjects.

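### The baseline rule is tied to the date of the first dose: read literally, it replaces Day 1 pre-infusion vital signs with screening values and conflicts with the plan's own Baseline window

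*Combined protocol and SAP*

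**What the plan says.** Section 9.4.1.2 allows for exceptions and otherwise states that "the baseline value will be defined as the measurement prior to and closest to the date of the first dose of JR-171". It does not mention the start of the infusion, or Day 1 values taken before it.

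Section 9.4.1.3 and the Schedule of Activities (Section 1.3) place the Baseline visit on Day -2 to Day 1. Screening runs from "28 days before Day 1 (Day -28) to Day -7" in Part 1 and over the same days in Part 2.

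For vital signs, the schedule footnote to the Baseline visit reads "Only body weight is measured" in both parts. The Week 1 footnote reads "Perform before and after administration of JR-171 except for body weight".

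For samples and tests at the Baseline visit, the Part 1 footnote begins "Perform before administration of JR-171 (or before laronidase at Week 5", and Part 2 has an equivalent. Section 8.5.1 adds that "CSF will be collected from each subject once before administration of JR-171 at the initial administration".

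For serum HS/DS, Section 8.5.5 asks the eCRF to hold "whether or not a measurement has been performed and, if applicable, the sample collection date should be recorded", with no time. Under Section 9.4.1.5, missing values: "they will be handled as missing and will not be imputed".

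The only explicit exception found is in Sections 1.1 and 3, which use screening data as baseline for BVMT-R/HVLT-R, T.O.V.A. and PedsQL-FIM.

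**The concern.** A rule that requires a measurement to precede the date of the first dose excludes anything measured on that date, even when it was taken before the infusion. The rest of the plan treats Day 1 before the infusion as a proper time for baseline assessments, so the definition and the schedule disagree.

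Change in vital signs is an endpoint under the primary objective, and Section 9.4.3 summarizes it as change from baseline. If the rule is programmed as written, that change starts from a visit one to four weeks before treatment, although pre-infusion values from the day of treatment exist. Section 9.4.4 uses a baseline plasma concentration in deriving PK parameters, and the only sample that can supply it is taken on Day 1.

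**Working it through.** The plan gives no figure to reproduce here. The check applies two rules to the pre-dose measurements in Section 1.3: (a) literal, measurement date earlier than the date of first dose; (b) last measurement before the start of the first infusion.

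**Gap to screening.** Day -28 is defined as 28 days before Day 1, so Day -7 is 7 days before it. A screening value is therefore 7 to 28 days old at first dose.

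| Measure | Screening | Baseline visit (Day -2 to Day 1) | Week 1 pre-dose (Day 1) | Rule (a) | Rule (b) |
|---|---|---|---|---|---|
| Pulse, temperature, blood pressure, respiratory rate, oxygen saturation | yes | no | yes | screening, always | Week 1 pre-dose |
| Plasma drug concentration | no | no | yes | none, always | Week 1 pre-dose |
| Laboratory tests | yes | yes | no | Baseline visit if Day -2 or -1; screening if Day 1 | Baseline visit |
| CSF, urine and serum HS/DS; antibodies; organ volumes; echocardiography; walk test (Part 2) | no | yes | no | Baseline visit if Day -2 or -1; none if Day 1 | Baseline visit |
| 12-lead ECG | yes | no | no | screening | screening |

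The first two rows do not depend on the day of the Baseline visit. For the five vital signs, rule (a) gives screening for every subject: 4 in Part 1 plus about 15 in Part 2, about 19 in all. The plasma row applies to subjects with PK sampling, which in Part 2 leaves out the first, dose-escalating subject in each paediatric age group. Body weight is set aside because it is not measured at screening.

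**Does another section repair this?**

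- Section 9.4.1.3 puts Day 1 inside the Baseline visit, which can be read as an exception for the laboratory and HS/DS rows. It does not help the vital signs or the plasma sample, because their Day 1 pre-dose values belong to Week 1, not to Baseline.
- The screening-baseline exception covers only the cognitive and family-impact tests.

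**Can the order on Day 1 be established?**

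- Infusion start time is recorded (Section 8.2.2), and so are times for vital signs (8.2.3), plasma samples (8.4.1) and the CSF drug sample (8.5.1).
- Only a date is required for laboratory tests (8.2.4), antibodies (8.2.5), and CSF, urine and serum HS/DS (8.5.2, 8.5.4, 8.5.5).
- Changing the test to on or before the date would not be safe. Vital signs are taken on Day 1 both before and after the infusion, so a post-infusion value could qualify.

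**Illustration only.** The 95% confidence interval half-width for a mean change, in SD units, is t(0.975, n-1)/√n: 1.049 at n=6, 1.242 at n=5, 1.591 at n=4 and 2.484 at n=3. If a Part 2 dose group of 6 lost one CSF baseline, the interval would be 1.242/1.049 = 1.18 times as wide; if it lost two, 1.591/1.049 = 1.52 times. In Part 1, losing one of 4 gives 2.484/1.591 = 1.56 times. The documents do not say how many subjects are sampled on Day 1, so these losses are assumptions.

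**The case against.** The strongest defence is that the plan should be read as a whole. Section 9.4.1.2 allows exceptions, the next subsection places Day 1 within Baseline, the schedule footnotes require the samples before dosing, and Section 8.5.1 ties the pre-dose CSF collection to the initial administration. A programmer using visit labels would accept a Day 1 sample as Baseline. Where order matters, several times are recorded. The CSF drug sample carries one, and it is natural, though not stated, that the HS/DS sample comes from the same lumbar puncture. Section 9.4 also describes itself as a summary and defers technical detail.

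Most of this stands for HS/DS. A reader might infer that subjects sampled on Day 1 lose their baseline and drop out of the paired CSF test, the trial's only hypothesis test, with intervals 18% to 56% wider. The documents do not support that as an expected result. It needs Section 9.4.1.2 to be read strictly and in isolation, and it needs a number of Day 1 samples that is not given. Nor is it right that the rule can only be programmed by comparing dates, since times exist for several measures.

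The defence does not reach the five vital signs or the plasma sample, because their Day 1 pre-dose values carry the Week 1 label. Whether deferred documents refine the rule cannot be checked; nothing supplied does so.

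A further point concerns the remedy. Day 1 pre-infusion vital signs may follow sedation for lumbar puncture (Section 8.5.2) or premedication (Section 6.1), so the choice of Day 1 is partly an analysis decision. It is, however, the choice that the plan's own preference for the closest measurement implies.

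**Conclusion.** The point holds as a conflict between the baseline definition and the plan's own schedule. Applied literally, the rule has two certain effects. The five non-weight vital signs take a baseline 7 to 28 days before the first dose for all of about 19 subjects, and the Week 1 pre-dose plasma sample cannot serve as baseline. The second matters to the extent that Section 9.4.4 means that sample, as it appears to. The vital-sign summaries are descriptive, so no test is affected. The size and direction of any shift in the summaries cannot be derived from the documents.

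For HS/DS, laboratory, antibody, imaging, echocardiography and walk-test values taken on Day 1 before dosing, two sections disagree. The intended answer can be inferred; only a strict reading would discard the value, and how often the case arises is unknown. The interval-widening figures show what a loss would cost, not what to expect. The definition should be corrected because it governs endpoints under the primary objective.

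**What to change.** Replace the definition in Section 9.4.1.2 along these lines:

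- Baseline is the last non-missing measurement before the start of the first JR-171 infusion, including values obtained on Day 1 before that infusion.
- For vital signs other than body weight, this is the Week 1 pre-administration value.
- A sample recorded by date only counts as pre-dose if the Schedule of Activities requires it before administration.
- BVMT-R/HVLT-R, T.O.V.A. and PedsQL-FIM keep their screening baseline.

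Section 9.4.4 should state that the baseline concentration is the Week 1 pre-dose sample, if that is what is meant.

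The cost is a wording change with no new data collection. The one judgement to confirm is that Day 1 pre-infusion vital signs are wanted even when sedation or premedication came first; if so, the plan should say it.
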